- continuously and systematically collect, evaluate, and archive relevant demographic and clinical information on patients belonging to chronic pain treatment centers, making it available for studies and research.
- promote the use of uniform and comparable classification systems, definitions, and records in the structures participating in the database.

- Define the flow of patients referring to pain therapy centers to allow adequate health planning and the priority areas of intervention of the national health plan.

The data collected will facilitate the planning of future studies aimed to:

- define the impact of chronic pain at a local and national level, and its territorial and temporal variations over time, through prevalence and incidence measures;
- identify clinical subtypes, risk factors, predisposing and triggering factors;
- increase knowledge in the field of chronic pain to standardize diagnostic/therapeutic pathways and promote adequate management strategies.

2. Objectives

Primary Outcomes

Identify the profiles of patients belonging to pain therapy centers in terms of:

1. Location and type of pain
2. Prescribed therapies
3. Effectiveness of therapies
4. Time needed to reach the efficacy outcome

Secondary Outcome

1. Evaluate the proportion of patients who reach the outcome of 30 or 50% improvement
2. Evaluate the healthcare resources used in terms of number of visits and time needed to achieve the best outcome (30 or 50% improvement)
3. Identify patient profiles that are related to clinically significant outcomes and the specific treatments performed, plus their intermediate surrogate outcomes in relation to specific patterns

4. Describe the relevant clinical variables in the study population. In particular, the absolute and relative frequencies of those clinical variables relevant to the effectiveness of the treatment will be described, categorized by type of treatment, and the timing of the start of treatment with respect to the onset of pain. The data collected may be used for predictive analyses.

3. Study Design

This is a prospective, multicenter, non-profit observational cohort study. No intervention on patients outside of common clinical practice is envisaged.

The study is divided into three phases.

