Phase 1, expected to last three months, involves the participation of 7 centers proposing the project and aims to structure the dataset and data entry methods. Actions will also be implemented for dissemination of the project by trying to recruit centers distributed across the national territory. Estimated start date 01/03/2023.

In phase 2, the project expands to the centers that wish to join, and this protocol will be fully operational.

The duration of phase 2 is two years and six months, presumably starting from 01/06/2023. Patient enrollment at each center will begin at different times depending on the rollout of the registry and local ethics committee approval. It is likely that the first patient will be prospectively enrolled in 01/06/2023. The last patient will be enrolled by 01/03/2025 and it will be possible to enter data and follow-up until 01/09/2025. The results of this study will be available by 01/12/2025.

Once the patient has been enrolled, it will be possible to trace the patient's personal file and update it at each follow-up until the end of enrollment.

In phase 3, SIAARTI will promote the register at the institutions for the establishment of a national register compliant with the DECREE OF THE PRESIDENT OF THE COUNCIL OF MINISTERS 3 March 2017 "Identification of surveillance systems and registers of mortality, tumors and other pathologies. (17A03142) (GU General Series n.109 of 12-05-2017)"

Setting

The study aims to collect demographic and clinical data from patients belonging to pain therapy centers recognized at the regional level and belonging to the pain therapy networks established in compliance with law 38/2010 and according to the Agreement between the Government and the Regions of 25 July 2012.

Patients will be registered regardless of the access modality (outpatient or hospitalization) and will be characterized by pathology and treatments performed. The participation of centers for the treatment of pediatric pain is expected. Data relating to patients under the age of 18 will be analyzed separately.

The database aims to follow the patients enrolled according to a code that makes them anonymous.

Participating Centers

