5. PROCEDURES EXPECTED AND INFORMATION COLLECTED

Enrollment procedure

Adult patients of both sexes who belong to pain therapy centers with a diagnosis of Chronic Pain (pain that lasts > 12 weeks), regardless of the etiology, modality and age of onset, will be considered eligible for enrollment.

It will be possible to enroll patients during their first visit (FIRST ANESTHESIOLOGICAL VISIT), or during a check-up visit (ANESTHESIOLOGICAL CHECK-UP VISIT) or during a scheduled hospitalization for pain procedures (ORDINARY OR DAY HOSPITAL ADMISSION)

Patients will be asked to join the study after having been informed in detail (also with the aid of a written information form) of the objectives of the project, as well as the methods with which these objectives will be pursued. Participants will be informed about the lack of informative feedback regarding the results of future clinical evaluations: the results of any research originating from the register, in fact, will not be delivered to the participants themselves. The subject who freely accepts will authorize the inclusion of their data in the project by signing the informed consent form of which they will receive a copy. It will also be clearly explained in the information sheet attached to the informed consent that each participant will have the possibility of withdrawing their participation from the study at any time, without providing any reason and without this jeopardizing the doctor-patient relationship with the specialists involved in the project.

Patients will be informed by the manager of the patient's pain center or the principal investigator for the center (assuming this is not the same individual).

The doctor will complete the electronic CRF after evaluating the patient and classifying him according to the criteria of the IASP (International Association for the Study of Pain) in terms of primary or secondary chronic pain. In the case of a patient enrolled during a check-up or during hospitalization, all data relating to the time in which the patient is in care at the center, the

invasive procedures previously undertaken, the drugs prescribed, will be collected. Retrospective data (only for patients already being treated at the center) will be collected according to a predefined group (e.g.: the patient has been in the care of the center for: > 5 years; from 1 to 5 years; from 1 year to 6 months; from 3 to 6 months; < 3 months).

[figure not shown]
Follow-up procedure

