6. ENDPOINT

Primary Endpoint

The number of patients referring to the centers, the type of pain, the proportion of patients who reach the clinically significant outcome, the type of therapies prescribed (pharmacological, neuromodulatory or implanted) necessary to achieve the outcome and the number of accesses and the Time in which a clinically significant improvement will be achieved (Change in BPI-s or BPI-I; a reduction of > 30% is considered clinically significant and a reduction of > 50% is considered optimal, the data will be evaluated for each Item).

Secondary Endpoint

1. The effectiveness of the treatments will be described in terms of
 - a. Change in pain intensity according to the Brief Pain Inventory-Severity questionnaire (BPI-S) A reduction of > 30% is considered clinically significant and optimal a reduction > of 50% the data will be evaluated for each Item)
 - b. b. Change in pain interference on daily activities according to the Brief Pain Inventory-Interference questionnaire (BPI-I). A reduction of > 30% is considered clinically significant and a reduction of > 50% is considered optimal; the data will be evaluated for each item)
2. Proportion of patients achieving clinically significant outcomes in relation to baseline characteristics and specific treatments performed and their intermediate surrogate outcomes in relation to specific patterns.
3. Resources used: Number of visits to the center for each patient in a year; Number of ordinary or day hospitalizations for each patient in a year.
4. The clinical variables relevant to the outcome will be described (e.g. type of pain, comorbidities, the time between treatment and clinically significant improvement, type of therapy undertaken - pharmacological, invasive, implant-based)

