12. ETHICAL CONSIDERATIONS

This observational study is designed and will be conducted according to the current protocol, in accordance with EU Directive 2001/20/EC relating to the implementation of the principles of good clinical practice in the conduct of clinical trials on medicinal products for human use, in accordance with the principles published in Good Clinical Practice (GCP) guidelines and in accordance with the Declaration of Helsinki on Ethical Principles for Medical Research Involving Human Subjects, adopted by the General Assembly of the World Medical Association (1996),

The investigator guarantees that personal patient data will be protected and processed in accordance with the General Data Protection Regulation (EU) 2016/679 (GDPR) on data protection and privacy.

ATTACHMENT 1

DATA GATHERED FOR EACH PATIENT

- ◇ CENTER CODE
- ◇ UNIQUE PATIENT CODE
- ◇ ACCESS METHOD (TO BE COMPLETED ONLY THE FIRST TIME FOR EACH PATIENT)
- ◇ DATE (the CRF must be filled in each time the patient has a visit/admission)
- ◇ SENT BY:
 - FAMILY DOCTOR
 - OTHER SPECIALIST
 - ADVICE FROM A RELATIVE/ACQUAINTANCE
 - WEB SEARCH
- ◇ REFERRAL METHOD (TO BE COMPLETED ONLY THE FIRST TIME FOR EACH PATIENT)
 - ◇ FIRST ANESTHESIOLOGICAL VISIT
 - ◇ ANESTHESIOLOGICAL CHECK-UP EXAMINATION
 - UNDER CARE AT THE CENTER FOR:
 - > 5 years;
 - from 1 to 5 years;
 - from 1 year to 6 months; or 3 to 6 months;
 - < 3 months
 - ◇ ORDINARY HOSPITALIZATION
 - IN EMPLOYMENT AT THE CENTER FOR:
 - > 5 years;
 - from 1 to 5 years;
 - from 1 year to 6 months; or 3 to 6 months;
 - < 3 months
 - ◇ DAY HOSPITALITY (DAY SURGERY OR DAY HOSPITAL)
 - IN EMPLOYMENT AT THE CENTER FOR:
 - > 5 years;
 - da 1 a 5 anni;
 - da 1 anno a 6 mesi; o da 3 a 6 mesi;
 - < 3 mesi

LEVEL 1: DEMOGRAPHICS

- ◇ AGE
- ◇ SEX
 - M
 - F

STATE/COUNTY OF RESIDENCE

SCHOOL LEVEL

- ◇ Not Known
- ◇ Grade School
- ◇ High School
- ◇ University

WORK

- ◇ WORKER
- ◇ UNEMPLOYED

COMORBIDITIES

- ◇ CARDIOVASCULAR
- ◇ DIABETES
- ◇ RESPIRATORY
- ◇ AUTOIMMUNITY
- ◇ CHRONIC INFLAMMATION
- ◇ OTHER

LEVEL 2: DIAGNOSIS

TYPE OF PAIN

- ◇ PRIMARY CHRONIC
 - CHRONIC WIDESPREAD PAIN
 - FIBROMYALGIA
 - OTHER
 - CRPS

- HEADACHE OR OROFACIAL PAIN
- MUSCULOSKELATAL
 - LOW-BACK PAIN
 - ALTRO
- ◇ SECONDARY CHRONIC
 - ONCOLOGICAL
 - POSTSURGICAL
 - LUMBAR
 - CERVICAL
 - BREAST
 - INGUINAL HERNIA
 - THORACOTOMY
 - OTHER
 - POST TRAUMATIC
 - CRPS
 - OTHER
 - NEUROPATHIC
 - PERIFERAL
 - POST-TRAUMATIC
 - DIABETIC
 - TRIGEMINAL
 - POST-HERPETIC

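### The healthcare-resource outcome is counted in different units and over different windows in Sections 2 and 6, and its yearly count cannot be observed for late enrollees

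*Protocol*

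**What the plan says.** Three places in the protocol bear on resource use.

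- Section 2, Secondary Outcome 2: "Evaluate the healthcare resources used in terms of number of visits and time needed to achieve the best outcome", the best outcome being a 30 or 50% improvement.
- Section 6, Primary Endpoint: "the number of accesses and the Time in which a clinically significant improvement will be achieved". The term accesses is not defined there, and the count is not labelled as resource use.
- Section 6, Secondary Endpoint 3: "Resources used: Number of visits to the center for each patient in a year; Number of ordinary or day hospitalizations", the latter also per patient and year. These are two separate counts.

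On terms, Section 3 (Setting) says "Patients will be registered regardless of the access modality (outpatient or hospitalization", so access there covers both routes. Section 5 (Enrollment procedure) lists a first visit, a check-up visit "or during a scheduled hospitalization for pain procedures (ORDINARY OR DAY HOSPITAL ADMISSION" as separate occasions for enrolment. Attachment 1 requires that "the CRF must be filled in each time the patient has a visit/admission", but it marks the items on access method and referral method, the latter separating first visit, check-up, ordinary hospitalization and day hospital, for completion on the first occasion only.

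**The concern.** One concept has definitions that differ in what is counted and in when counting stops. A resource figure from this registry will depend on which definition the analyst picks.

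The choice of unit can also act unevenly across treatments. Section 5 ties scheduled admissions to pain procedures. A count that leaves admissions out is therefore lower for procedure-treated patients than for drug-treated patients with the same number of contacts. Sections 2 and 6 plan to relate outcomes to the specific treatments given, and Section 1 names health planning as a purpose of the database, so such a comparison is likely to be made and used.

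A fixed yearly count also presumes a year of observation, which the protocol's own dates do not give every patient.

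**Working it through.** The protocol gives no resource figure to reproduce. The check compares the definitions and then the follow-up dates.

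**1. Definitions side by side**

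| | Section 2, Secondary Outcome 2 | Section 6, Primary Endpoint | Section 6, Secondary Endpoint 3 |
|---|---|---|---|
| Event counted | visits | accesses (undefined) | visits; separately, ordinary or day hospitalizations |
| Counting stops at | 30 or 50% improvement | clinically significant improvement | one year |
| Called resource use | yes | no | yes |

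**2. Effect of the unit (illustrative counts, not from the protocol)**

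Patient A reaches improvement after 2 visits and 2 day-hospital admissions. Patient B reaches it after 4 visits.

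- Section 2, visits excluding admissions: A = 2, B = 4.
- Section 2, visits including admissions: A = 4, B = 4.
- Primary endpoint, accesses read as in Section 3: A = 4, B = 4.

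In general, visits-only count = total contacts × (1 − share that are admissions). For A this is 4 × (1 − 2/4) = 2, which is 50% low. For assumed admission shares of 10%, 30% and 50%, the count is low by the same percentages. The difference between A and B arises only on the narrow reading of visits.

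**3. Effect of the window**

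If A and B each have 4 further visits later in the year, the counts to improvement do not change. The yearly counts become 2 + 4 = 6 visits and 2 admissions for A, and 4 + 4 = 8 visits for B. This difference does not depend on how visits is read.

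**4. Can a year be observed?**

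Inputs: Section 3 gives enrolment from 01/06/2023 to 01/03/2025 (21 months) and data entry until 01/09/2025 (6 months after the last enrolment). Section 5 (Follow-up procedure) gives 12 months of enrolment and closes the database 3 months after the last enrolment. Assumptions: uniform accrual, follow-up to database close, and a constant contact rate.

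Let T be the accrual months and c the months open after the last enrolment.

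- Share with under 12 months = (12 − c)/T.
- Mean follow-up in that group = (12 + c)/2 months.
- Shortfall of an unadjusted count in that group = 1 − (mean follow-up)/12.
- Shortfall in the overall mean = share × that shortfall.

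| Timeline | Share under 12 months | Mean follow-up in that group | Shortfall in that group | Shortfall overall |
|---|---|---|---|---|
| Section 3: T = 21, c = 6 | 6/21 = 29% | 9 months | 25% | 7% |
| Section 3 accrual, Section 5 close: T = 21, c = 3 | 9/21 = 43% | 7.5 months | 37.5% | 16% |
| Section 5: T = 12, c = 3 | 9/12 = 75% | 7.5 months | 37.5% | 28% |

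On the Section 3 dates the affected patients are those enrolled after 01/09/2024. Sections 3 and 5 also each say that follow-up runs to the end of enrolment, which would shorten it further. Section 3 expects centers to start at different times; that would tend to push enrolment later and raise these shares.

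**5. Can hospitalizations be counted?**

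Each contact produces a dated form, so total contacts can be counted. No field listed in Attachment 1 says whether a contact after the first was a visit or an admission. As listed, the split that Secondary Endpoint 3 needs is available only for the enrolment contact.

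**The case against.** A reader might infer that Section 2 counts outpatient visits only. The word outpatient is not there. Section 5 (Follow-up procedure) speaks of entering data at each visit while Attachment 1 asks for a form at each visit or admission, so visit may mean any contact. The enrolment procedure, Secondary Endpoint 3 and Attachment 1 do keep visits and admissions apart, so the narrow reading is reasonable, but it remains an inference. Access is also partly inferred: in Section 3 it describes how patients present and is not a counting unit. The text is a translation, and a change of word may carry no intent.

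A reader might also conclude that day-hospital therapies look cheaper. No costs are collected, only contacts, so the documents do not support a statement about cost.

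Nor is it right that resources to improvement go unmeasured. The primary endpoint counts accesses to improvement, so Section 6 already holds both a count to improvement and a yearly count. That an early responder and a never-responder can share a yearly figure is a property of any utilisation count and no error.

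Finally, the analysis is descriptive, no decision rule rests on this outcome, and counting rules can be left to an analysis plan; *in a year* may be meant as a rate. These points limit the severity. They do not reconcile the unit and window that the protocol itself states in Sections 2 and 6. An analysis plan also cannot recover a contact type that was never recorded.

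**Conclusion.** The point holds as an inconsistency of definition with two practical consequences. It should be corrected before data entry.

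- **Certain from the text:** the window differs between Section 2 (to improvement) and Secondary Endpoint 3 (a year), and the terms for the unit differ across three places without definition.
- **Conditional:** the understatement for procedure-treated patients arises only if visits excludes admissions. Its size equals the share of contacts that are admissions, which the protocol does not give; 10 to 50% is an assumed range.
- **From the protocol's dates, under uniform accrual:** 29% of patients on the Section 3 dates, and up to 75% on the Section 5 timeline, cannot supply a full year. If their counts were tabulated unadjusted at a constant contact rate, the overall mean would be low by about 7% to 28%. If contacts cluster soon after enrolment, the shortfall is smaller.
- **From Attachment 1 as listed:** hospitalizations after enrolment cannot be told apart from visits. The electronic form may hold a field that the attachment does not show.

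**What to change.** State the same two outcomes in Sections 2 and 6.

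1. **Accesses to improvement.** Define an access as an outpatient visit, a day-hospital admission or an ordinary admission. Count accesses from enrolment to the first > 30% reduction and to the first > 50% reduction, by type and in total. Treat patients who do not improve as censored at their last contact and do not drop them; the result can be shown as the cumulative proportion improved by access number. Name the BPI item or score that defines the reduction, since Section 6 evaluates every item. Show patients enrolled at a first visit separately from those already in care, because counting starts at enrolment and not at the start of care.
2. **Overall use.** Report visits and admissions per patient-year of observation, whether or not the patient improved. This replaces the count in a year and uses every patient's actual follow-up. Reconcile the Section 3 and Section 5 follow-up periods so that the observation time is defined.

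In Attachment 1, make contact type (first visit, check-up, day hospital, ordinary hospitalization) a required field on every visit or admission form.

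The cost is protocol wording, one repeated field and one extra table. Censoring assumes that patients who stop attending would have improved at the same rate as those who continue, and the report should say so.

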Once enrolled, the patient will be followed prospectively until the end of enrollment. At each visit it will be possible to retrieve the patient's chart and fill in the data relating to the intensity of pain and the treatments undertaken. It will also be possible to modify or add an etiological diagnosis in forms of secondary chronic pain. There is no limit to the number of follow-ups for each patient as long as the database is active (3 months from the date of enrollment of the last patient, considering a 12-month active enrollment expected for this study).

Data gathered

The activities of the registry do not replace routine diagnostic tests or visits to your doctor. The data collected by the registry will include relevant demographic data of the patient, comorbidities, the duration of the pain (> 5 years; from 1 to 5 years; from 1 year to 6 months; from 3 to 6 months), the type of pain, the location of the pain, the intensity of the pain (Brief Pain Inventory- Severity (BPI-S) and pain interference in daily activities (Brief Pain Inventory- Interference (BPI-I), treatments received (categorized according to pharmacological therapy, infiltrative therapy, ablative or neuromodulatory therapy, implants), the tests conducted, the number of other medical specialists contacted for the pathology being studied, the professional who sent it to the center. Specifically, the data collected is shown in Attachment 1
In particular, patients will be characterized by:

Type of pain (chronic primary or chronic secondary according to the scheme proposed by IASP)

Location of pain according to the following scheme (multiple options are possible)

- Lower back pain
- Thoracic
- Upper arts
- Lower limbs
- Head/Neck
- Pelvis

Pain Intensity

Brief Pain Inventory-Severity (BPI-S)

Interference with daily activities

Brief Pain Inventory-Interference (BPI-I)

Clinical information related to the pathology

Therapy
Pharmacological
Infiltrative
Implantable

Data collection methods and anonymization

The data collected will be used for scientific and epidemiological purposes. Each data will be created by a participating center and recorded on the SIAARTI Servers via a web application using the RedCap® data management software.

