8. STATISTICAL ANALYSIS

All enrolled patients registered in the registry will be included in the analyses. A descriptive analysis will be performed on the collected data. In general, qualitative variables will be described using frequency distributions; the quantitative variables will be described by mean and standard deviation if normally distributed, and by median and interquartile range if asymmetrically distributed. As appropriate, statistical tests will be used for exploratory purposes. Treatment effects (Change in BPI-S and BPI-I scores) will be calculated as the ratio of the difference between baseline and follow-up scores to the baseline score. If the data allow it, inferential analysis will be applied on quantitative data (such as: comparison of Student's t means, Fisher's F, etc.), or on qualitative data (such as: chi square, odds ratio, Mann Whitney U, etc.). The prevalence of the different pathologies and the related confidence intervals will be estimated. Detailed statistical analysis plans will be set up in future research protocols that will use this database as a source of data.

Sample Size

Since this is an observational registry, no prior sample size calculation is required. Considering an expected participation of 12 centers, an estimate of 2500 patients included appears reasonable.

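### Secondary Endpoint 3 counts contacts per patient in a year, but late entrants have less than a year, the enrolment contact has no rule, and later contacts carry no type

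*Protocol*

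**What the plan says.** - **Endpoint (Protocol, Section 6, Secondary Endpoint 3):** "Number of visits to the center for each patient in a year; Number of ordinary or day hospitalizations for each patient in a year". The start of the year is not given, nor whether it is a calendar or a patient year.
- **Analysis set (Section 8):** "All enrolled patients registered in the registry will be included in the analyses". No minimum follow-up and no person-time denominator is stated.
- **Calendar (Section 3):** enrolment is expected to start on 01/06/2023. On its close, Section 3 says "The last patient will be enrolled by 01/03/2025 and it will be possible to enter data and follow-up until 01/09/2025". Centres open in stages: "Patient enrollment at each center will begin at different times depending on the rollout of the registry and local ethics committee approval".
- **Other follow-up ends:** Section 5, Follow-up procedure, says "Once enrolled, the patient will be followed prospectively until the end of enrollment", and Section 3 likewise has the file updated until enrolment ends. The same part of Section 5 keeps the database active for "3 months from the date of enrollment of the last patient, considering a 12-month active enrollment expected for this study".
- **Entry (Section 5, Enrollment procedure):** patients join at a first visit, at a check-up, or at a scheduled ordinary or day-hospital admission.
- **Recording (Attachment 1):** a dated CRF is completed at each visit or admission. The items for access method and referral method, which separate first visit, check-up, ordinary admission and day admission, are completed only the first time for each patient.

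**The concern.** The endpoint reads as a count over one year in every enrolled patient, yet part of the cohort cannot be observed for a year. A raw count then understates their use of the centre. How far depends on enrolment date, and so on when a centre joined.

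The enrolment contact works the other way. Patients are found through a visit or an admission. If that contact is counted, every check-up entrant has at least one visit and every admission entrant at least one hospitalisation because of how they were recruited.

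The endpoint also needs visits and hospitalisations apart, and the listed dataset separates them only at entry.

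Section 1 wants patient flow described for health planning, so these figures are meant to be used at face value.

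**Working it through.** The protocol gives no figure for this endpoint to reproduce. The expected 2500 patients (Section 8) serve only to scale shares. The protocol gives no accrual curve, so even enrolment is an assumption.

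**1. Who lacks a year.** Enrolment from 01/06/2023 to 01/03/2025 is 639 days.

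Share short = (last enrolment − (follow-up end − 1 year)) / enrolment length.

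Coverage = 1 − share short × (1 − mean fraction of the year observed among those short).

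| Follow-up end | Short if enrolled after | Share short | Of 2500 | Shortest follow-up | Coverage |
|---|---|---|---|---|---|
| 01/09/2025 (Section 3) | 01/09/2024 | 181/639 = 28.3% | 708 | 184 days | 0.930 |
| 3 months after last patient, on Section 3 enrolment dates | 01/06/2024 | 273/639 = 42.7% | 1068 | 92 days | 0.840 |
| End of enrolment, 01/03/2025 (Sections 3 and 5) | 01/03/2024 | 365/639 = 57.1% | 1428 | 0 days | 0.714 |
| 12 months of enrolment plus 3 (Section 5) | month 3 | 9/12 = 75% | 1875 | 3 months | 0.719 |

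First row: those short have on average (365 + 184)/2 = 274.5 days, or 0.752 of a year, so coverage = 1 − 0.283 × 0.248 = 0.930. Last row: 3/12 × 1 + 9/12 × 7.5/12 = 0.719.

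**2. Sensitivity to accrual.** Centres open in stages, so enrolment may be weighted late. If the rate rises linearly from zero, the share short at 01/09/2025 is 1 − (458/639)² = 48.6%. For the second and third rows it is 67.2% and 81.6%. If a calendar year is meant, only 2024 lies wholly inside the dated period, and 425/639 = 66.5% enrol after 01/01/2024 under even accrual.

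**3. Can the year be completed backwards?** No. For patients already in care, Section 5 collects banded time in care, earlier invasive procedures and drugs prescribed. Neither Section 5 nor Attachment 1 asks for the number of earlier visits or admissions.

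**4. The enrolment contact.** Let r be the true yearly rate of further contacts and T the years observed. Including the enrolment contact, the expected count is 1 + rT, and scaled to a year it is (1 + rT)/T = r + 1/T. The excess is 1 per year at T = 1, 2 at T = 0.5 and 4 at T = 0.25, whatever r is. With r = 2 (assumed), the results are 3, 4 and 6 instead of 2. Scaling short follow-up to a year without removing the enrolment contact therefore enlarges the error. The excess falls on visits for patients who enter at a visit and on hospitalisations for those who enter at an admission. For 12-month hospitalisations the mean excess per patient equals the proportion entering at an admission, which the protocol does not give.

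**5. Contact type.** After the first CRF, Attachment 1 supplies a date, pain scores, examinations and therapy. A therapy entry may suggest a procedure but does not say whether the contact was a visit, an ordinary admission or a day admission.

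**The case against.** The strongest reply is that a yearly figure per patient can be read as an annual rate. Including all enrolled patients is compatible with person-time, and annualising incomplete follow-up is often left to an analysis plan. This stands in part. A reader might infer that annual resource use cannot be estimated for late entrants; the documents do not support that, because only the full-year count is out of reach. Still, the text fixes a yearly count and names no denominator, and no analysis plan can lengthen follow-up or supply a contact type that was not collected.

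Second, on the Section 3 calendar the shortfall is only about 7% of patient-years, in a descriptive secondary endpoint. That is correct. The larger shares come from other follow-up ends in the same protocol.

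Third, nothing says that the enrolment contact is counted. It is real workload, and its route is recorded, so it could be removed at analysis. That too is fair. A reader might infer that the plan inflates hospitalisations by some large percentage, but the protocol gives neither an admission rate nor the mix of entry routes. What remains is that the contact is on record for everyone and no rule says how to treat it.

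**Conclusion.** The point holds as a gap in the endpoint's definition and its data capture. On the most generous follow-up end, about 28% of patients lack a full year and raw counts reach about 93% of the intended patient-years. Both figures assume even enrolment. Later-weighted enrolment or the shorter follow-up ends raise the share short, which cannot be settled until Sections 3 and 5 agree.

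The effect of the enrolment contact is conditional on its being counted, and its size is unknown. That centres differ is plausible, given staggered starts and several entry routes, but the documents do not show it.

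The missing contact type rests on no assumption about accrual: on the listed items, hospitalisations after the first contact cannot be counted apart from visits. A change is worth making before data collection, at a weight suited to a descriptive secondary endpoint.

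**What to change.** 1. **Redefine Secondary Endpoint 3** as the number of contacts after the enrolment contact per person-year of observation, in all enrolled patients, with visits, ordinary admissions and day admissions reported separately. Person-time runs from enrolment to data close, or to withdrawal if earlier.
2. **Use one rule for every entry route:** leave the enrolment contact out of the rate, for first-visit entrants as well, and report enrolment contacts separately by route.
3. **Add a supporting figure:** the 12-month count in patients enrolled at least 12 months before data close (by 01/09/2024 on the Section 3 dates).
4. **Complete the existing contact-type item on every CRF**, not only the first. Without this, the separate rates in step 1 cannot be produced.
5. **Reconcile the follow-up ends** in Sections 3 and 5 (6, 0 and 3 months after the last patient) and the enrolment lengths (21 and 12 months).

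The cost is a short rewrite of the endpoint and one existing item repeated at each contact. The supporting 12-month count uses about 72% of patients (458/639, about 1792 of 2500) under even enrolment on the Section 3 dates; the rate uses everyone.
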